## REVISION HISTORY

Version No.	Version Date	Description of Modifications
0.1	22Jul2014	[REDACTED]
0.2	28Apr2017	[REDACTED]
0.3	22May2017	[REDACTED] [REDACTED] [REDACTED] [REDACTED]
1.0	31May2017	[REDACTED]

## List of Abbreviations

AE	Adverse event
CI	Confidence interval
CS	Clinically significant
ECG	Electrocardiogram
ITT	Intent-to-treat
LS	Least square
MedDRA	Medical Dictionary for Regulatory Activities
NCS	Not clinical significant
NE	Not estimable
PT	Preferred term
RBC	Red blood cell
SAE	Serious adverse event
SD	Standard deviation
SE	Standard error
SGIS	Subject's Global Impression of Severity
SOC	System Organ Class
TEAE	Treatment-emergent adverse event
WBC	White blood cell
WHODD	World Health Organization Drug Dictionary

## 1. Introduction

The purpose of the Statistical Analysis Plan is to provide a framework that addresses the protocol objectives in a statistically rigorous fashion with minimized bias or analytical deficiencies. Specifically, this plan has the following purpose:

- To prospectively (a priori) outline the types of analyses and data presentations that will address the study objectives outlined in the protocol.
- To explain in detail how the data will be handled and analyzed, adhering to commonly accepted standards and practices of statistical analysis in the pharmaceutical industry.

## 2. Objectives

The objective of this trial is [REDACTED] in alleviating spasticity [REDACTED].

## 3. Investigational Plan

### 3.1. Overall Study Design and Plan

This is a double-blind, [REDACTED] [REDACTED] a single [REDACTED], in subjects with spasticity due to MS. [REDACTED].

Upon completion of informed consent, at the start of [REDACTED]  
[REDACTED]  
[REDACTED]  
[REDACTED]  
[REDACTED]  
[REDACTED]  
[REDACTED]  
[REDACTED]. Safety and efficacy assessments will be performed according to the schedule of events in Section 11.5. [REDACTED]

[REDACTED] following the completion of exit assessments.

### **3.2. Study Endpoints**

#### **3.2.1. Efficacy Endpoints**

##### **Primary Efficacy Endpoint:**

[REDACTED] Total Modified Ashworth Score over time [REDACTED]. The primary efficacy endpoint of the study [REDACTED] Total Modified Ashworth Scores [REDACTED] [REDACTED] assessed on Days 23 and 24.

##### **Secondary Efficacy Endpoints:**

- [REDACTED] spasm frequency
- [REDACTED] nighttime awakening score
- [REDACTED] Clinical Global Impression of Change (CGIC) score on [REDACTED]
- [REDACTED] Subject's Global Impression of Severity (SGIS) [REDACTED]

#### **3.2.2. Safety Endpoints**

- Adverse events (AEs)
- Vital signs
- 12-lead electrocardiogram (ECG)
- Laboratory tests

- Columbia Suicide Severity Rating Scale (C-SSRS)

#### **4. General Statistical Considerations**

In general, continuous variables will be summarized with descriptive statistics (number of observations, mean, standard deviation, median, minimum, maximum, and 95% CI) and categorical variables will be summarized with count and percentage, unless otherwise specified. If there is only one observation, the standard deviation will be displayed as NE (Not Estimable). The p-values will be two-sided and rounded to four decimal places, and a significance level of alpha ( $\alpha$ ) = 0.05 will be used to reject the null hypothesis. Baseline will be defined as the last pre-dose non-missing measurement, unless specified otherwise.

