## **7. Treatments and Medications**

### **7.1. Prior and Concomitant Medications**

A medication will be categorized as prior medication if the medication end date is before the first dose date. A medication will be categorized as a concomitant medication if the medication end date is after the first dose date or is ongoing at study completion. If the start or end date of a medications is missing, it will be imputed as described in Appendix 11.4. All prior and concomitant medications will be coded to Anatomical Therapeutic Chemical (ATC) Class 3 and Preferred Name according to the latest version of the World Health Organization Drug Dictionary (WHODD).

The number and percentage of subjects in the Safety population taking prior or concomitant medications will be summarized by ATC class and Preferred Name in two separate tables, by dose group and overall. In addition, the prior medications for MS and spasticity, and the medications subjects washed out from in order to enter the study, as well as neurological and anti-spasticity concomitant medications, and concomitant medications present at Day 23 check-in will be summarized separately. Antispasticity and neurological medications will be identified via a Medial Monitor review of coded terms prior to database lock. Subject listings of prior and concomitant medications will be provided. The medications taken within 30 days prior to the screening visit will be listed in a separate listing.

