### **7.2. Study Treatments**

[REDACTED]  
[REDACTED]  
[REDACTED] Duration of exposure will be summarized descriptively using number, mean, standard deviation, median, minimum and maximum at [REDACTED], by dose group and overall. Counts and percentages will be provided for subjects exposed for [REDACTED]

Study treatment compliance rate will be calculated as the ratio of the total number of tablets taken to the total number of tablets assigned, where the total number of tablets taken is ( [REDACTED] ). [REDACTED]

[REDACTED]

[REDACTED]

[REDACTED]

[REDACTED]

[REDACTED]

[REDACTED]. A subject listing of study treatment compliance will be provided.

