### **9.3. Vital Sign Measurements**

Seated diastolic and systolic blood pressures and resting pulse measurements at baseline and each post-baseline timepoint will be summarized using descriptive statistics. Similarly, change from baseline to [REDACTED] will also be summarized. Change from baseline summaries will use subjects who have both a baseline and a post-baseline value present and will include an additional baseline mean and standard deviation summary for those subjects present. The change from baseline for vital sign measurements will be shown in a boxplot. The investigators will assign a rating of NCS or CS to all vital sign values. The CS clarification requires reporting of the vital sign value as an AE. Vital sign values will be displayed in a data listing with CS results flagged.

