### **9.5. Electrocardiogram**

ECG recordings will be collected at screening, [REDACTED], [REDACTED], [REDACTED]. ECG measurements will be collected in triplicate, [REDACTED] will be calculated for ECG intervals (QT, PR, RR QRS, ventricular rate). The QT interval will be corrected for heart rate using Fridericia's correction (QTcF) and Bazett's correction (QTcB). ECG intervals will be summarized using descriptive statistics. In addition, change from baseline in ECG intervals and shift from baseline in overall ECG interpretation (Normal, Abnormal – NCS, Abnormal – CS) will be provided. Change from baseline summaries will use subjects who have both a baseline and a post-baseline value present and will include an additional baseline mean and standard deviation summary for those subjects present. All ECG results will be displayed in a data listing and the ECG abnormalities will be flagged out.

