## 11.5. Schedule of Study Procedures

Subject will check-out of the clinic following the [REDACTED] .

Subjects will be required to be currently receiving prior to enrollment, and

Hematology: red blood cell (RBC) count, hemoglobin, total white blood cell (WBC) count, differential WBC count, platelet count; serum chemistry: sodium, potassium, chloride, blood urea nitrogen (BUN), creatinine.

4 Within 2 hours

23 or 24 hours post-dose

Within 10 minutes of 12-lead ECG

Dosing at time “0”

Within 2 hours pre-dose

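### Does a default baseline that omits the word *first* put an on-treatment value under the vital-sign and ECG changes?

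*Combined protocol and SAP*

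**What the plan says.** The general rule is in SAP Section 4: "Baseline will be defined as the last pre-dose non-missing measurement, unless specified otherwise". It applies wherever a later section does not set its own baseline.

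Several sections do. Section 8.1 defines a baseline for the total Modified Ashworth Score (the time point is redacted). Section 8.2 uses the screening visit for spasm frequency and nighttime awakening. Section 9.2 places laboratory tests at screening and Day 24 and compares against screening.

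Vital signs and ECG have no such definition in the readable text. Section 9.3 says that blood pressures and "resting pulse measurements at baseline and each post-baseline timepoint will be summarized using descriptive statistics". Section 9.5 calls for "change from baseline in ECG intervals and shift from baseline in overall ECG interpretation".

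The features that suggest more than one dose are these:

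- Section 7.2 computes compliance as "the ratio of the total number of tablets taken to the total number of tablets assigned" and also summarises duration of exposure.
- The primary endpoint is "assessed on Days 23 and 24".
- Section 7.1 states that "concomitant medications present at Day 23 check-in will be summarized separately".
- The Section 11.5 footnotes set dosing at time zero and include the timings "Within 2 hours pre-dose" and "23 or 24 hours post-dose".

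**The concern.** In a single-dose study the rule would be unambiguous. With repeated dosing, pre-dose can refer to any dose. The schedule footnotes use the term relative to a particular timed dose, and a window of 23 or 24 hours after dosing would fit a clinic stay over Days 23 and 24. If vital signs or ECGs were taken shortly before a dose in that stay, the latest pre-dose reading would come after treatment had started. Section 7.1 does write first dose date when it sorts prior from concomitant medications, so the missing word in Section 4 is noticeable.

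The stake would be the safety tables. A change measured from an on-treatment reading leaves out whatever shift in blood pressure, pulse or corrected QT had already built up. The ECG shift table could record a subject who had become abnormal on treatment as unchanged.

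**Working it through.** No figure in the plan depends on the baseline rule, so there is nothing to reproduce. The randomised total of about 135 in Section 4.1 is the same under either reading. The check is one line of algebra followed by a comparison of the sections.

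1. **What the literal reading would cost.** Let B be the value before the first dose, P a value before a later clinic dose, and T a value after that dose. Put X = P − B and Y = T − P. The change from a pre-treatment baseline is T − B = X + Y. The literal rule would report T − P = Y. The share of the change that is lost is f = X/(X + Y), taking X and Y in the same direction. With f = 0 nothing is lost, with f = 0.5 half is lost, and with f = 1 all of it is. The documents give neither X nor Y, so f cannot be narrowed within 0 to 1.

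2. **Whether a value P exists for these measures.** The loss arises only if vital signs or ECGs were recorded before a later dose. The schedule grid in Section 11.5 is not shown, so the footnote "Within 2 hours pre-dose" cannot be tied to either row or to any day. It could belong to the first dose. The ECG times after screening (Section 9.5), the vital-sign change time point (Section 9.3) and the start of dosing are redacted. The text neither shows such a measurement nor excludes one.

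3. **Which reading the safety sections fit.** Section 9.3 sets baseline against every later time point, which is natural if baseline precedes treatment. Sections 9.3 and 9.5 restrict changes to subjects with both values and repeat the baseline mean and SD for that subset. Section 9.2 gives the reason for the same device: dropout after screening. At the planned 30% rate, 0.30 × 135 ≈ 40 subjects could be missing later, so the device is needed when baseline is early. Between a pre-dose and a post-dose reading in one clinic stay there would be little attrition to handle. This is not conclusive, because under the literal rule an early dropout would still have an earlier value as baseline. Baseline would then mean pre-treatment for dropouts and on-treatment for completers, a mixture that nothing in the plan suggests is intended.

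4. **Whether leaving out *first* carries meaning.** Section 9.1 identifies pre-existing conditions by reference to drug administration and drug treatment, also without *first*, and plainly means before any study drug. The omission in Section 4 matches that usage, so the contrast with Section 7.1 is weak evidence of a different intent.

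5. **What the default rule reaches.** The primary endpoint, two secondary endpoints and the laboratory summaries are outside it. Vital signs and ECG remain, summarised descriptively and also listed by subject. The C-SSRS and SGIS text is too heavily redacted to tell which reference value is used. No hypothesis test in the readable text is shown to depend on the default.

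**The case for a change.** The best argument for a change is that it costs one word. Two programmers could follow the same sentence and produce different vital-sign and ECG tables. The error, if made, would tend to hide an accumulated effect on a safety endpoint. Since the intended baseline is almost certainly the one before any study drug, writing it down would lose nothing.

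Part of this stands. The sentence is loose, repeated dosing is a fair inference from the tablet counts and the Day 23 check-in, and adding *first* would be a harmless editorial choice. What does not stand is the step from a loose sentence to a wrong table. That step needs a vital-sign or ECG reading before a later dose, which the documents do not show, and an analyst who would call an on-treatment reading baseline in a table of change on treatment. Any account of weeks on drug, trough levels or steady state would add facts about dosing that the readable text does not give.

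**Conclusion.** No change is needed. This is a small gap in wording that analysts fill sensibly: in a safety table, baseline means the last value before the first dose of study drug, and the surrounding sections fit that meaning. Stating it would record what would be done anyway, and no result is shown to move.

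The potential loss is confined mainly to the descriptive vital-sign and ECG summaries, and its size cannot be computed from the documents. The conclusion assumes that pre-dose is read in its ordinary sense, and that redacted text in Sections 9.3, 9.5 and 11.5 does not set a different baseline. If the full schedule did show these measurements before a later dose, the looseness would be more than theoretical for those tables. The primary endpoint, spasm frequency, nighttime awakening and laboratory summaries would still be unaffected.

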##### **4.1. Sample Size**

[REDACTED]

[REDACTED] 31 evaluable subjects in each treatment group is required to provide 90% power, assuming a common standard deviation [REDACTED]. To account for the drop-out rate of 30%, approximately 135 subjects will be randomized in this trial.

##### **4.2. Randomization, Stratification, and Blinding**

Eligible subjects will be randomized to receive [REDACTED]

[REDACTED].

[REDACTED]

[REDACTED]

[REDACTED] as required for regulatory reporting

purposes. [REDACTED]  
[REDACTED]

### **4.3. Analysis Sets**

Two analysis sets will be used in this study:

- The Intent-to-Treat (ITT) population consists of all subjects who are randomized to a treatment, who receive [REDACTED]  
[REDACTED]  
[REDACTED]. Subjects in this population will be analyzed according to the treatment they were randomized to, regardless of any dosing error.  
[REDACTED]
- [REDACTED]  
[REDACTED]  
[REDACTED]  
[REDACTED].

## **5. Subject Disposition**

### **5.1. Disposition**

Subject disposition will be listed and summarized for all enrolled subjects, by dose group and overall. The number and percentage of subjects who were screened, were randomized, and who are in the ITT and Safety populations will be summarized. The number and percent of subjects who completed and who discontinued the study will be summarized. The reasons for study discontinuation will be summarized for the categories below:

- Adverse Event
- Major Protocol Violation
- Lost to Follow-Up
- Worsening of Condition

- Other Reasons

## **5.2. Protocol Deviations**

Protocol violations (i.e., divergences from the inclusion and exclusion criteria, received excluded concomitant medications, received wrong treatment or incorrect dose, and those who developed withdrawal criteria but were not withdrawn) and deviations (i.e., non-adherence to trial procedures or schedule) will be recorded on the CRF and tracked in a deviation log. Protocol violations will be summarized in a table for the ITT population, by dose group and overall. Protocol violations and deviations will be displayed in a listing.

## **6. Demographics and Baseline Characteristics**

### **6.1. Demographics**

Subject demographics, including age, [REDACTED] sex, race and ethnicity, will be summarized with descriptive statistics for the ITT and Safety populations, by dose group and overall. Listings of individual subjects' data will also be produced.

### **6.2. MS Medical History**

The MS medical history at screening will be summarized by [REDACTED]

[REDACTED] ITT and Safety Populations, by dose group and overall. This information will also be presented in a data listing.

### **6.4. Inclusion and Exclusion Criteria**

All inclusion/exclusion information on enrolled subjects will be included in a by-patient listing. The listing will include a flag indicating whether all criteria were satisfied. For subjects who did not satisfy the criteria, the criteria number will be listed with the deviation

## **7. Treatments and Medications**

### **7.1. Prior and Concomitant Medications**

A medication will be categorized as prior medication if the medication end date is before the first dose date. A medication will be categorized as a concomitant medication if the medication end date is after the first dose date or is ongoing at study completion. If the start or end date of a medications is missing, it will be imputed as described in Appendix 11.4. All prior and concomitant medications will be coded to Anatomical Therapeutic Chemical (ATC) Class 3 and Preferred Name according to the latest version of the World Health Organization Drug Dictionary (WHODD).

The number and percentage of subjects in the Safety population taking prior or concomitant medications will be summarized by ATC class and Preferred Name in two separate tables, by dose group and overall. In addition, the prior medications for MS and spasticity, and the medications subjects washed out from in order to enter the study, as well as neurological and anti-spasticity concomitant medications, and concomitant medications present at Day 23 check-in will be summarized separately. Antispasticity and neurological medications will be identified via a Medial Monitor review of coded terms prior to database lock. Subject listings of prior and concomitant medications will be provided. The medications taken within 30 days prior to the screening visit will be listed in a separate listing.

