### **9. Safety Analysis**

Safety evaluations will be based on the incidence, severity, and causality of AEs, vital signs, Columbia-Suicide Severity Rating Scale C-SSRS, electrocardiogram (ECG), and clinical laboratory results. The safety analysis for female subjects will also include urine pregnancy results. All safety analyses will be conducted on the Safety population.

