### **9.1. Adverse Events**

Treatment-emergent adverse events (TEAEs) will be used for summary and analysis purposes. A TEAE is defined as: any new event that occurred [REDACTED] [REDACTED] [REDACTED], a condition that existed before drug administration but increased in severity, or a condition that existed prior to drug treatment but increased in frequency of occurrence. A treatment-emergent serious adverse event (SAE) is defined as any treatment-emergent event that results in death, is immediately life threatening, requires inpatient hospitalization or prolongation of existing hospitalization, results in persistent or significant disability/incapacity, is a congenital anomaly/birth defect, or is an important medical event. TEAEs will be recorded [REDACTED]. [REDACTED] will be coded to System Organ Class (SOC) and Preferred Terms (PTs) using the latest version of of MedDRA®.

A treatment-related AE is an event that is considered possibly or probably related to study drug, in the judgment of the investigator. If the AE start date is missing, it will be imputed as described in Appendix 11.4.

The following summaries of AEs by SOC and PT will be provided:

- Overall TEAE summary, including:
  - Incidence of subjects with one or more TEAE
  - Incidence of TEAEs by highest relationship
  - Incidence of TEAEs by highest severity
  - Incidence of TEAEs by action taken
  - Incidence of TEAEs by outcome
  - Incidence of treatment-emergent SAEs

- TEAEs by SOC and PT
- TEAEs by descending order of frequency of PTs
- TEAEs by SOC and PT and highest relationship to treatment
- Treatment-related TEAEs by SOC and PT
- TEAEs by SOC and PT and highest severity
- Treatment-related TEAEs by SOC and PT and highest severity
- TEAEs by SOC and PT and sex
- TEAEs by SOC and PT and age group
- TEAEs by SOC and PT and race
- TEAEs by SOC and PT and frequently used concomitant medications (i.e., medications used by 20% or more of the subjects overall)
- TEAEs by SOC and PT and concomitant medications present on [REDACTED]
- TEAEs leading to treatment discontinuation by SOC and PT
- SAEs by SOC and PT
- Fatal SAEs by SOC and PT
- Treatment-related SAEs by SOC and PT

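### Section 7.1 leaves a medication that ended on the first dose date neither prior nor concomitant, so it drops out of both medication tables

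*Combined protocol and SAP*

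**What the plan says.** Section 7.1 of the SAP sorts medications by end date relative to first dose. A drug is a "prior medication if the medication end date is before the first dose date". It is a "concomitant medication if the medication end date is after the first dose date or is ongoing at study completion". For incomplete dates the section adds: "If the start or end date of a medications is missing, it will be imputed as described in Appendix 11.4".

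The two labels then drive the output. The number and percentage of Safety population subjects "taking prior or concomitant medications will be summarized by ATC class and Preferred Name in two separate tables", by dose group and overall. Section 7.1 also plans separate summaries that use the same words, among them "the prior medications for MS and spasticity" and "neurological and anti-spasticity concomitant medications".

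Section 9.1 carries the concomitant label into a safety table: "TEAEs by SOC and PT and frequently used concomitant medications (i.e., medications used by 20% or more of the subjects overall"). Section 9 states that "All safety analyses will be conducted on the Safety population".

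**The concern.** The two definitions should together cover every medication with a known end date, each exactly once. They do not, because one uses strictly before and the other strictly after, and the day between them belongs to neither. That day is the first dose date, when a drug being stopped, or given once, can overlap with study treatment.

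A programmer who follows the text literally omits the record from both tables. One who notices the gap must choose a category that the plan does not state, and two programmers could choose differently. At stake is the completeness of the medication tables, and of the adverse event table split by commonly used concomitant drugs. The primary and secondary efficacy analyses are not at stake: nothing visible in Section 8 is shown to depend on these labels.

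**Working it through.** **Inputs**

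- Prior and concomitant rules: Section 7.1.
- Scope of the imputation appendix: its citation in Section 7.1 and its title in the table of contents, both confined to partial or missing dates.
- Planned number randomized, about 135: Section 4.1.
- Threshold of 20% of subjects for a frequently used concomitant drug: Section 9.1.
- Safety population size: not known, because the definition in Section 4.3 is redacted. Using 135 is an assumption; 120 and 100 are illustrations only.

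The plan gives no figure of its own on this point, so there is none to reproduce.

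**Step 1: run the rules over the possible cases.** Let d = end date minus first dose date, in whole days. Prior requires d < 0. Concomitant requires d > 0, or ongoing at study completion.

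| Case | Prior? | Concomitant as written? | Concomitant if d ≥ 0 or ongoing? |
|---|---|---|---|
| d = −2 | yes | no | no |
| d = −1 | yes | no | no |
| d = 0 | **no** | **no** | yes |
| d = 1 | no | yes | yes |
| d = 2 | no | yes | yes |
| Ongoing | no | yes | yes |

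Only d = 0 is unassigned. The ongoing clause does not rescue it, since a drug that ended on the first dose date is not ongoing at study completion. With d ≥ 0 in the concomitant rule, every known end date falls in exactly one category and no other row changes.

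**Step 2: look for another rule that assigns d = 0.** Appendix 11.4 is invoked when a date is missing; here the date is known. No other visible section assigns the record.

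**Step 3: effect on a percentage.** An affected subject with no other qualifying record of the drug lowers that drug's overall percentage by 1/n:

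- n = 135: 1/135 = 0.74 points
- n = 120: 1/120 = 0.83 points
- n = 100: 1/100 = 1.0 point

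The tables are also given by dose group, where the denominator is smaller and one subject weighs more.

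**Step 4: effect on the 20% threshold in Section 9.1.** At n = 135 the cut-off is 0.20 × 135 = 27 subjects.

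- True users 27, one uncounted: 26/135 = 19.3%, so the drug leaves the table (27/135 = 20.0% would have kept it).
- True users 28, one uncounted: 27/135 = 20.0%, so the drug stays and only that subject's subgroup membership changes.

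The usual effect is therefore that one subject is missing from a drug's subgroup. Loss of the drug from the table needs a count exactly at the cut-off.

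**The case against.** The strongest reply has four parts.

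- **The appendix cannot be read.** The body of Appendix 11.4 is not in the public text, so a classification rule inside it cannot be strictly excluded. That is fair as a limit on certainty. But its title and its citation both confine it to dates that are not fully known, and a reader of Section 7.1 would have no reason to look there for a known date.
- **An undefined day is not yet a wrong count.** An omission occurs only if such records exist and both strict operators are programmed literally. The first condition stands: there may be no such record. The second is simply what following the plan means. The medical review of coded terms before database lock and the subject listings might bring such a record to light, but neither is stated as a safeguard for this date.
- **Some downstream effects are inferred.** Section 7.1 does not say whether the MS, spasticity and neurological summaries are derived from the date rule or from separate case report form fields. That stands. They use the same two words as the definitions, so the date rule is the natural reading, but it is a reading.
- **The direction of the repair is a convention.** Assigning the day to prior would also close the gap. That is correct as logic. It would, however, label as prior a drug given after the first dose on the same day, whereas the concomitant label keeps possible overlap visible in the safety tables.

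**Conclusion.** The gap is real on the plain wording, and it is exactly one calendar date wide. Followed as written, a medication with a known end date equal to the first dose date is counted in neither of the two main medication tables, and its user can drop out of the matching subgroup in the Section 9.1 table.

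The size is small and cannot be determined from the documents: the number of affected records is unknown and possibly zero, and the percentages above depend on an assumed Safety population size. The conclusion assumes that Appendix 11.4 does what its title says. It makes no claim about the subject listings, the summary of washed-out medications, the Day 23 check-in summary, or drugs with no recorded end date. The correction is worth making because it is nearly free; it does not affect how the trial's efficacy results are read.

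**What to change.** In Section 7.1, change the concomitant rule to: *end date on or after the first dose date, or ongoing at study completion*. Leave the prior rule as it is. Records with no end date continue to depend on Appendix 11.4 and are not altered.

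The cost is one phrase in the SAP and one operator in the program (> becomes ≥). There is a small downside: the rule works on dates, not times, so a drug last taken before dosing on the first dose day will count as concomitant. An anti-spasticity drug stopped that morning would thus appear in the concomitant anti-spasticity summary. A footnote to the affected tables can say so.
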